# 9.5.2 Statistical Analyses of Efficacy Measurements

## 9.5.2.1 Primary Efficacy Analysis

The primary endpoints are listed below:

- Change from baseline in PVR after 22 weeks of treatment
- Change from baseline in 6 MWD after 22 weeks of treatment.

The primary efficacy hypothesis regarding the superiority of APD811 to placebo will be assessed in a stepwise manner. First, the statistical significance of APD811 versus placebo result will be determined for the change from baseline in PVR at the end of 22 weeks of treatment. If the result is significant (p < 0.05, two-sided), the primary hypothesis will be considered satisfied and this study will be declared positive. Subsequently, the change from baseline in 6MWD will only be tested if the change from baseline in PVR is significant. This testing procedure preserves the overall Type I error rate for testing the primary efficacy hypothesis.

An analysis of covariance (ANCOVA) model with baseline PVR as a covariate and treatment and baseline WHO/NYHA functional class as factors will be used to assess the effect of APD811 on change from baseline in PVR. Missing values will be imputed using the last observation carried forward (LOCF) method. Assumptions for the analysis of covariance will be checked, and if not satisfied, parametric analyses will be corroborated with nonparametric analyses or with appropriate data transformations if necessary (i.e., log transformation).

Six minute walking distance (6MWD) will be analyzed using the above ANCOVA method described for PVR, substituting the relevant baseline measurement as the covariate. Missing values will be imputed with last observation carried forward, except if any patient withdraws early due to death or due to clinical worsening without a 6MWT being measured at a termination visit, a worst value of 0 for 6MWD will be imputed.

Note that testing for secondary and exploratory endpoints will proceed only if the comparison for the change from baseline in PVR is significant.

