7 STATISTICAL TECHNICAL ISSUES

7.1 Planned Statistical Power and Sample Size

For the APD811 versus placebo comparison, 28 patients in the APD811 group and 14 patients in the placebo group will have 90% power to detect a between-treatment difference of 350 dyn·s·cm⁻⁵ in PVR. This calculation was based upon the pooled SD estimate of 320.3 dyn·s·cm⁻⁵ for the mean change from baseline in PVR at Week 17 observed in the selexipag phase 2 study.

Assuming that up to 30% of patients may drop out of the trial before a post-randomization repeat RHC is performed, 40 patients will be randomized to the APD811 group and 20 patients will be randomized to the placebo group. For 6MWD, 40 patients in APD811 group and 20 patients in the placebo group will have 80% power to detect a between-treatment difference of 50 meters in 6MWD assuming pooled SD estimate of 65 meters.

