7.2 Method of Assigning Study Participants to Treatment Groups

Patients who meet all the entry criteria and are eligible for the study will report to the investigator to be randomized on Day 1. At the beginning of the dose titration period, eligible patients will be randomly assigned to receive 1 of 2 study treatments, either APD811 or placebo in a 2:1 ratio. Sites will randomize approximately 60 patients for entry into the study using an Interactive Web Randomization System (IWRS) across the entire study, and is not constrained within a center. Randomization will be stratified by Baseline WHO/NYHA Functional Class (Class II vs. III or IV).

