7.4 Handling of Missing Data and Sensitivity Analysis

For the ITT analysis of PVR missing week 22 assessments will be derived using the method of multiple imputation via the SAS/STAT procedure PROC MI and the fully conditional

specification (FCS) method to create 100 imputations resulting in 100 complete datasets. The 100 imputed datasets will then be analyzed using the methods described in Section 4.3.1, with the results of the analyses performed on the 100 datasets combined via PROC MIANALYZE. The imputation model will include the following variables: treatment, baseline PVR, baseline NYHA/WHO functional class category, baseline PAH therapy, baseline values for 6MWD, BNP, NT-proBNP, etiology, last on-treatment 6MWD and whether or not a patient experienced clinical worsening. It is anticipated that the imputation model will converge but should it not do so terms will be removed from the model to achieve convergence. The effects of any such model adjustment will be investigated.

To assess the impact of missing data and robustness of the results, the following sensitivity analyses will be performed for the primary, secondary and selected exploratory endpoints:

- Completers population analyses on primary and secondary efficacy endpoints will be performed without missing data imputation.
- Worst case imputation. For PVR, in all-treated patients, prior to ANCOVA analyses as detailed in Section 4.3.1 missing data at Week 22 due to any reason will be imputed by taking:
 - the worst percentage change from baseline in all patients regardless of treatment group.
 - the baseline observation carried forward.
- An additional 'tipping point analysis' *may* be performed for PVR, post-hoc, in the event that the primary analysis is statistically significant and at least 1 of the worst case imputation analyses yields a non-significant result.

For the proportion of patients who progress to clinical worsening, a sensitivity analysis to assess the impact of missing data will be performed wherein all patients who prematurely discontinue treatment for any reason will be considered to have had a clinical worsening event.

- Imputation of missing or incomplete AE start date
 - If year part of AE start date is missing, then the year of the first treatment date will be assigned.
 - If both month and day part of AE start date are missing, and the year part is the same as year of the first treatment date, then the first treatment date will be assigned;

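### The both-arm 'worst case' rule for missing PVR is not a worst case for APD811: its bias follows the difference in missingness, and the tipping-point analysis is optional and conditional

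*SAP*

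**What the plan says.** The primary PVR analysis is multiple imputation under a missing-at-random (MAR) assumption, with treatment in the imputation model (SAP 4.3.1, 7.4 and Appendix 4). RHC values from early withdrawal are used when they exist.

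SAP 7.4 then lists sensitivity analyses:

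- A completers analysis without imputation.
- Two imputations under the label *worst case*, covering values missing for any reason. One assigns "the worst percentage change from baseline in all patients regardless of treatment group". The other carries baseline forward, so the change is 0.
- A tipping-point analysis that *may* be done post-hoc, and only "in the event that the primary analysis is statistically significant and at least 1 of the worst case imputation analyses yields a non-significant result". The SAP gives no penalty range and does not say which arm would be penalised.

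SAP 9 also keeps the protocol's MITT analysis as a sensitivity analysis. On the extent of missingness, SAP 7.1 says: "Assuming that up to 30% of patients may drop out of the trial before a post-randomization repeat RHC is performed". Allocation is "either APD811 or placebo in a 2:1 ratio" (SAP 7.2), with 40 and 20 patients randomized.

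**The concern.** For a superiority claim, a worst case is an assumption unfavourable to the new drug. A rule that gives the same bad value to missing patients in both arms does something else. Each missing APD811 patient pulls the estimate away from APD811, and each missing placebo patient pushes it towards APD811. The net result mainly reflects which arm lost more RHCs, not how far MAR can fail before the conclusion changes.

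Up to 30% of the primary endpoint may be imputed, so readers will lean on this check. If placebo happens to lose more values, an analysis labelled worst case can look better than the observed data. The one analysis that would vary MAR in a controlled way may then never be run, because it waits for one of the two imputations to fail.

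**Working it through.** **Inputs from the documents.** Two-sided alpha 0.05 (Protocol 9.5.2.1). Difference 350 and SD 320.3 dyn·s·cm⁻⁵ (dyn below), 28/14 evaluable, 40/20 randomized (SAP 7.1).

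**The plan's own figure.** The SAP states that "28 patients in the APD811 group and 14 patients in the placebo group will have 90% power". The standard error is 320.3 × √(1/28 + 1/14) = 104.8, and 350/104.8 = 3.34. Power is 91.6% by normal approximation and 90.3% by noncentral t. Then 28/0.7 = 40 and 14/0.7 = 20. The figure reproduces, and it implies 30% missing in each arm.

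**Expected estimate under the both-arm rule.** Let mA and mP be the missing fractions, μA and μP the true mean changes, and W the mean change assigned to missing patients. A negative difference favours APD811.

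Difference = (1 - mA)μA - (1 - mP)μP + (mA - mP)W

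The last term is the bias from the shared value. It is zero when mA = mP.

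**Simulation.** 2,500 runs per cell; 40/20 patients; normal changes; values missing completely at random; ANCOVA on baseline PVR; observed-data analysis standing in for the MAR primary. The documents give no baseline PVR distribution. The assumption is a mean of 600 to 1200 with CV 40%; results with a constant baseline are in square brackets.

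| Missing APD811, placebo | True effect | Estimate, both-arm rule | Significant for APD811 |
|---|---|---|---|
| 12/40, 6/20 | 0 | about 0 | 0.2% or less |
| 12/40, 6/20 | 350 | -246 [-244] | 29-30% [45%] |
| 4/40, 6/20 | 0 | -205 [-143] | 22-24% [18%] |
| 4/40, 6/20 | 350 | -465 [-427] | 99% [99.7%] |
| 2/40, 6/20 | 0 | -257 [-184] | 45-48% [38%] |
| 12/40, 2/20 | 0 | +200 [+142] | about 0% |
| 12/40, 2/20 | 350 | -86 [-128] | about 2% |

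The formula explains the table:

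- Equal 30%, true 350: 0.7 × (-350) = -245, with no W term. Observed data would be significant in 89-90% of runs with varying baseline.
- 4/40 against 6/20, no effect: (0.1 - 0.3)W = -0.2W. The simulated -205 [-143] implies W of about 1025 [715].
- 4/40 against 6/20, true 350: 0.9 × (-350) - 0.2W = -315 - 0.2W. The simulated -465 [-427] implies W of about 750 [560].
- A 10-point gap, 8/40 against 6/20, true 350: 0.8 × (-350) - 0.1W = -280 - 0.1W. With W of 560 to 750 this is -336 to -355, so the check no longer stresses the result.

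**How likely is a gap?** Take independent binomial counts, 40 and 20 patients, 30% risk in each arm. The placebo fraction exceeds the APD811 fraction by at least 10 points with probability about 24%, and by at least 20 points with probability about 7%.

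**The trigger.** At 4/40 against 6/20 with a true 350, the tipping-point condition is met in 0.2% of runs or fewer. Baseline carried forward does not inflate: its estimate is about 0.9 × (-350) = -315. It is nonetheless significant in about 97% of runs, so it seldom opens the gate. As an extreme benchmark, giving the worst value to missing APD811 patients only would overturn a significant primary result in 50-52% [37%] of the same runs. At equal 30% missing with a true 350 the condition is met in about 59-62% [46%] of runs, and the analysis would still be optional.

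**The case against.** A reader might infer that the rule generally manufactures a benefit for APD811. The documents do not support that. The plan's own assumption is equal missingness, where the rule is harsh on APD811, and with more APD811 missing it is harsher still. Unequal drop-out alone is not enough; the excess must be on placebo.

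Nor do the documents predict such an excess. RHC is asked for at early termination (Protocol 6.8). Placebo patients who worsen need the end-of-study RHC to enter the extension (Protocol 6.9), which works against missing placebo values. The 4/40 against 6/20 pattern is an illustration. The binomial calculation shows only that a gap can arise by chance, and a gap in the other direction is about as likely.

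A reader might also infer a higher false-positive rate for the trial. That does not follow: the study is declared positive on the primary PVR test, and the 18-24% refers only to this sensitivity analysis. Nor does the both-arm rule alone control the tipping point, because a non-significant baseline-carried-forward result also opens it.

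Finally, treating every missing patient as a failure is a legitimate symmetric analysis. The SAP does the same for 6MWD after death or worsening without a test, and when it counts all discontinuations as clinical worsening. That stands. The fault is the label and the reliance placed on the rule, not its existence.

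**Conclusion.** The concern holds in a limited form. The both-arm rule is not a worst case for the superiority claim, and its direction is set by the sign of mA - mP. It can hide fragility when more placebo values are missing, and the analysis that would reveal this is optional, post-hoc, unspecified and gated.

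The sign and the dependence on mA - mP need only that the worst observed change is an increase in PVR. The sizes rest on the assumed baseline PVR, normal changes and missingness completely at random, so the percentages are indicative. This is a worthwhile improvement to a supportive analysis and does not undermine the primary test.

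**What to change.** In SAP 7.4:

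1. Pre-specify a delta-adjusted multiple imputation that is always run. Impute placebo under MAR. Add a fixed penalty to imputed APD811 changes only, from 0 to +350 dyn in fixed steps such as 50. Report the delta at which significance is lost, or state that it is not lost within the range. The upper end removes the whole planned effect from the imputed patients: at 30% missing, the expected estimate is -350 + 0.3 × 350 = -245.
2. Delete *may*, *post-hoc* and the trigger.
3. Relabel the both-arm rule as the same poor outcome for all missing patients, and report it with missing counts by arm.

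A single worst value for APD811 only should not be the main stress test. At 12/40 and 6/20 missing it turns a true 350 into about -21 to -28 [-75], significant in about 0.5% [1%] of runs, so it would nearly always fail even if the drug works as planned.

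The cost is SAP wording and a small addition to the Appendix 4 program, which adds delta to imputed APD811 values before the ANCOVA step. No new data are needed and the primary analysis is unchanged. There is slightly more analysis work, and the robustness result may look less favourable.

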
Patient Population:
	
Up to 60 patients with PAH will be studied.
 
All women, regardless of childbearing potential, must have a negative pregnancy test at Screening (serum hCG) and on Day 1 (urine dipstick) of the dose titration period and periodically throughout the study (serum hCG).
 
Males and females of childbearing potential must use adequate means of contraception and must agree not to participate in a conception process (i.e., active attempt to become pregnant or to impregnate, sperm donation, in vitro

	fertilization) for 1 month after the last dose of study drug.
Duration per Patient:	~29 weeks: 4 weeks for screening, a 22 week treatment period including a dose titration period of up to 9 weeks, followed by a 3 week follow-up visit. Patients will stay on treatment through the follow-up visit if continuing into the open-label extension study. For patients not continuing into the open-label extension study, treatment will be discontinued at the end of the treatment period.
Patient Assignment:	Patients will be randomly allocated to APD811 or placebo in a 2:1 ratio.
Sample Size:	Up to 60 patients.
Efficacy Assessments:	
Efficacy will be assessed by measurement of pulmonary vascular resistance (PVR) obtained on RHC, measurement of B-type natriuretic peptide (BNP), N-terminal pro-brain natriuretic peptide (NT-proBNP) levels and six-minute walk test (6MWT).
 
Primary:
 
 • Change from baseline in PVR • Change from baseline in 6MWD 
Secondary:
 
 • Percent change from baseline in PVR • Proportion of patients who exhibit clinical worsening 
Exploratory:
 
 • Change from baseline in BNP/NT-proBNP • Change from baseline in WHO/NYHA functional class • Change from baseline in other hemodynamic parameters (e.g. SVR)
Pharmacokinetic Assessments:	
Dose Titration Period: Pharmacokinetic (PK) blood samples will be collected pre-dose and at 4 hours post-dose at each dose escalation, and one week after the last dose escalation.
 
Treatment Phase: PK blood samples will be collected pre-dose and at 4 hours post-dose at each visit during the treatment phase.
 
An additional blood sample for PK analysis will be collected if possible at the time of any intolerable AE or SAE.

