5.3 Adverse Events

Adverse events will be coded using the most current Medical Dictionary for Drug Regulatory Affairs (MedDRA) and tabulated, including categorical information of interest such as onset and resolution times, time of onset relative to dose, severity at onset, maximum severity, causal

relationship to study medication, and action taken. AEs will be regarded as ‘pre-treatment’ if they occur between screening and the time of administration of the first dose of APD811 or placebo and will be recorded as medical history. All other AEs that occur or worsen after the first dose of study medication will be considered to be ‘treatment-emergent’. Missing or incomplete start date of AE will be imputed as section 7.4.

Treatment-emergent AEs (TEAE) will be listed by patient and by treatment. They will be summarized per treatment and expressed in terms of maximum severity and relationship to study medication. The incidence of TEAEs classified according to system organ class will be summarized by treatment group. TEAEs will also be summarized by maximum intensity (assessed according to the Common Terminology Criteria for Adverse Events v4.03² definitions) and relatedness to study medication.

Summaries of the number (%) of patients in each treatment group with at least 1 TEAE, classified according to MedDRA system organ class and preferred term, will also be provided for:

- Drug-related TEAE
- Treatment-emergent AEs leading to permanent discontinuation of study medication (study medication discontinued or withdrawal from study).
- Serious adverse events (SAEs)
- Prevalence of selected treatment-emergent AEs over dose titration and treatment periods

Serious adverse events will be listed by patient and by treatment. If there are no SAEs at the end of the study, the tables or listings will state that there are no SAEs in the study.

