 - If both month and day part of AE start date are missing, and year part is less than the year part of the first treatment date, then 'Dec31' will be assigned to the missing month and day part

- If both month and day part of AE start date are missing, and year part is greater than year part of the first treatment date, then 'Jan01' will be assigned to the missing month and day.
- If month part is present and day part is missing, and year and month are same as year and month of the first treatment date, then the first treatment date will be assigned;
- If month part is present and day part is missing, and year and month combination is before the year and month combination of the first treatment date, then the last day will be assigned;
- If month part is present and day part is missing, the year and month combination is after the year, month combination of the first treatment date, then '01' will be assigned to the missing day.

After imputing: if the date of AE end a complete date, and the imputed ASTDT is later than the date of AE end, then reassign AE start date as AE end date.

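### When the AE start year is missing but the month is recorded, SAP 7.4 can date an on-treatment event months before first dose and drop it from the TEAE tables

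*SAP*

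**What the plan says.** SAP 7.4 lists rules for incomplete AE start dates. The first is "If year part of AE start date is missing, then the year of the first treatment date will be assigned". It carries no condition on the recorded month, the AE end date or the treatment window.

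Later rules then act on whatever year results:

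- Month and day both missing, "and the year part is the same as year of the first treatment date, then the first treatment date will be assigned".
- Month recorded but day missing, where the "year and month combination is before the year and month combination of the first treatment date, then the last day will be assigned".
- Month and day both recorded: no further rule applies, so the date stands once the year is filled in.

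One check follows imputation. If the end date is complete and "the imputed ASTDT is later than the date of AE end, then reassign AE start date as AE end date".

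SAP 5.3 makes these dates decide the safety tables: "Missing or incomplete start date of AE will be imputed as section 7.4". The pre-treatment class holds AEs where "they occur between screening and the time of administration of the first dose of APD811 or placebo and will be recorded as medical history". For the rest, "All other AEs that occur or worsen after the first dose of study medication will be considered to be" treatment-emergent. The SAP synopsis gives the exposure as "a 22 week treatment period including a dose titration period of up to 9 weeks".

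**The concern.** The missing-year rule settles an unknown by assumption. In a patient whose treatment runs over New Year, an AE recorded as February with no year is far more likely to belong to the February on treatment than to the one many months before first dose. The rule always chooses the earlier one. Neighbouring rules behave differently: where the recorded parts cannot separate before from after first dose, they assign the first treatment date.

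The stake is an event missing from the treatment-emergent summaries. Safety and tolerability are a secondary objective in Protocol 2.2, assessed in about 40 patients on APD811 and 20 on placebo. If a lost record is a patient's only event of a given term, the incidence of that term changes by 1/40 = 2.5 percentage points on APD811 or 1/20 = 5 points on placebo.

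**Working it through.** The plan states no figure on this point, so the check applies its rules to dates.

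**Inputs.** The SAP 7.4 rules and end-date check; the SAP 5.3 definitions; treatment to Day 154, or to Day 175 ± 1 week for patients going into the extension (Protocol Table 2); AE monitoring for up to 30 days after dosing (Protocol 6.13.1); screening within 28 days of dosing (Protocol 6.16 and 7.1).

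**Step 1: one patient.** First dose 10 Nov 2015, true onset in February 2016.

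| Recorded start | Imputed start | Position |
|---|---|---|
| 03 Feb, no year | 03 Feb 2015 | before first dose |
| Feb, no day or year | 28 Feb 2015 | before first dose |
| nothing recorded | 10 Nov 2015 | first treatment date |

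A complete end date of 20 Feb 2016 does not help. The check acts only when the start is later than the end, and 03 Feb 2015 is not. The check can move a start date earlier, never later.

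**Step 2: all dates.** The rules were applied to every first-dose date in a 365-day year and every onset day in windows of 154, 175, 182 (175 + 7) and 212 (175 + 7 + 30) days. Each case was run without an end date and with a complete one 7 days after onset. For onsets after New Year with the year missing:

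- month and day recorded: 100% dated before first dose;
- month only recorded: 100%;
- nothing recorded: 0%.

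The end date changed none of these. Onsets in the same calendar year as first dose were never dated before it (0 of 48,650 date pairs in the 175-day window).

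**Step 3: how far back.** An onset d days after first dose, moved back one year, lands 365 − d days before first dose. At d = 212 that is 365 − 212 = 153 days. If the day is missing, the month-end rule can bring it forward by at most 30 days: 153 − 30 = 123. Both exceed 28, so the imputed onset always precedes the screening window.

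**Step 4: the opposite error.** First dose 10 Jan 2016, screening event recorded as 20 Dec with no year. The rule gives 20 Dec 2016, after first dose, so the event counts as treatment-emergent. A complete end date of 03 Jan 2016 pulls the start back to that day and the event is pre-treatment again. Without a complete end date before first dose, the error stays.

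**Step 5: exposure.** Assume entry is uniform over the year. A window of L days crosses 1 January for L − 1 of 365 first-dose dates:

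- L = 154: 153/365 = 42%;
- L = 175: 174/365 = 48%;
- L = 212: 211/365 = 58%.

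If onset is also uniform within the window, the share of onsets after New Year is (L − 1)/(2 × 365): 153/730 = 21%, 174/730 = 24%, 211/730 = 29%. Each share must still be multiplied by the proportion of AE records with a month but no year, which the documents do not give.

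**The case against.** The best defence is that this path will be nearly empty. It needs a recorded month, an absent year, first dose in the previous calendar year and onset after New Year. Protocol 6.13.1 has staff ask at scheduled times about the period since the last enquiry, so the visit date normally fixes the year. Protocol 8.1 expects all queries resolved at lock, and SAP 8.3 expects data reviewed and declared clean before unblinding. An onset months before screening should look odd to anyone reviewing it. All of this stands and lowers the severity. It does not make the rule correct, since the rule exists for records that cleaning failed to complete.

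A second defence is that the imputed date does not literally meet the SAP 5.3 pre-treatment definition, which starts at screening, and that Protocol 6.13.1 treats everything reported after dosing as treatment-emergent. Both observations are right. But an onset before screening is not an onset after first dose either, so under SAP 5.3 the event is still absent from the TEAE tables. The protocol sentence shows that the SAP rule can remove an event the protocol would count. The wording on worsening in SAP 5.3 would keep an event that later worsened, but not others.

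A reader might infer that every post-New-Year AE without a year is lost. That is not so, because a wholly missing date goes to the first treatment date. Nor do the documents support calling the error one-directional (Step 4 shows the reverse) or saying that it removes more events from one arm, for which they give no figure.

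**Conclusion.** Wrong as written, lowest severity. For a start date with the month recorded and the year missing, the rule misdates every on-treatment onset that falls after New Year in a patient first dosed the previous year. Unless the event later worsened, it leaves the TEAE tables. This follows from the text and needs no assumption.

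The size in this trial cannot be calculated from the documents. The number of such records is not given and is probably very small. The 42% to 48% rests on uniform entry, which is an assumption, and describes patients whose treatment crosses 1 January. It should not be read as a share of AEs misclassified. No effect on any conclusion of the trial is shown.

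**What to change.** Restrict the change to start dates with the year missing and the month recorded:

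1. Assign the earliest year that places the recorded month (and day, if known) on or after first dose, or in the first-dose month if the day is missing, and no later than the AE end date or last contact. Then apply the existing day rules.
2. If no year fits, assign the latest year that places the onset before first dose, and treat the event as pre-treatment.
3. Leave the first-treatment-date rule in place when the whole start date is missing.

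In the examples above, 03 Feb becomes 03 Feb 2016 and Feb alone becomes 01 Feb 2016, given an end date or last contact after those dates. For the December screening event, 20 Dec 2016 falls after the end date (or, if there is none, after a last contact in mid-2016), so the date becomes 20 Dec 2015 and the event is pre-treatment.

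The cost is a short amendment to SAP 7.4 and a derivation that reads the AE end date and last contact date. A small downside is that an occasional pre-treatment event will be counted as treatment-emergent.
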